### **7.5 Emergency Unmasking**

During the follow up study visit, if the outcome assessors discover any medical conditions or complications that require further attention, the participants will be referred back to the cataract clinic (for eye complications) or to their GP for any other medical concerns such as acute osteoarthritis needing review of medication. As the study visit takes place at three to six months after the surgery, post-operative complication regarding the IOL implantation or cataract surgery procedure is unlikely. In case it happens, the outcome assessors will be unmasked to the type of interventions received by the patients for further care by asking the patients directly, reviewing discharge summary or contacting CI who holds the randomization list.

### **7.6 Baseline data**

At each study visit based at the UoP, the participant's full name, DOB, address and contact details will be checked for identification purposes. These details will remain separate from the study data which will be identified using the unique study number allocated to the participants.

The outcome measures will include the following:

- General demographic information such as age, gender, ethnicity, relevant medical history, cataract diagnosis and vision assessment results. This will last about 10 minutes.
- Dynamic stability assessment lasts about 30 minutes. Three motion sensors will be put on the participants' body (neck, lower back and upper leg) and they will be asked to wear a special eye tracking glass (figure 1). After that, the participants will be asked to perform a Timed Up and Go (TUG) test which involves getting up from a chair, walking 3m-distance and return to sit back on the chair. They will also be asked to walk over obstacles on level ground and the last mobility task is walking up and down a standardized staircase. Movement outcomes will be measured using three-dimensional motion analysis

Vision and balance changes after bilateral implantation of Toric IOLs  
IRAS ID: 286913

(ProMove 3D, Inertia Technology, The Netherlands) and eye tracking data will be collected *via* Tobii-pro glasses 2 (Tobii AB, Sweden) (figure 2 and 3). Three trials will be taken to estimate the average and the best recorded time will be taken for the TUG test. As all the participants are active community dwelling elderly without mobility problem, the dynamic stability tasks are no more demanding than their usual daily activities. The PPI also include discussion about the demand of the assessment and all participants agreed the dynamic stability tests only required low level mobility and no concerns were raised.

- Some qualitative data will be collected *via* self-administered questionnaires which takes about 15 minutes. Risk of fall will be assessed with the short Fall Efficacy Scale (FES-short) and Fear of Falling questionnaire. Vision specific quality of life will be assessed with CAT-PROM 5 questionnaire.

- Standard visual function assessment will also be carried out to assess visual acuity and degree of astigmatism and this takes about 20 minutes.

A paper CRF has been prepared for this study to collect data directly relevant to the objectives and outcomes measures detailed in the protocol.

[figure not shown]
[figure not shown]

Figure 1. Set up with movement sensor and eye tracking device (a) and movement sensors placement reinforced with tape (b)

Vision and balance changes after bilateral implantation of Toric IOLs  
IRAS ID: 286913

Figure 2. Example of eyetracking analysis using Tobii pro lab software: a) study of gaze on defined area of interest (stool in this example) and b) heat map analysis

[figure not shown]

Figure 3. Example of movement sensor output data using Promove 3D software

Vision and balance changes after bilateral implantation of Toric IOLs  
IRAS ID: 286913

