### iii. TRIAL SUMMARY

Trial Title	Vision and balance changes after bilateral implantation of Toric versus non-Toric intraocular lenses in Cataract patients with astigmatism	
Internal ref. no. (or short title)	Vision and balance changes after bilateral implantation of Toric IOLs	
Clinical Phase	Pre and post operation comparison	
Trial Design	Randomised controlled trial	
Trial Participants	Ambulatory adult aged over 50 years with bilateral cataract patients and astigmatism >1.0D awaiting intraocular lens replacement surgery	
Planned Sample Size	140 participants	
Treatment duration	Up to 12 months after first eye surgery	
Follow up duration	12 months after second eye surgery	
Planned Trial Period	3 years	
	Objectives	Outcome Measures
Primary	
 
• Dynamic balance in functional activities
 
	
 
• Centre of mass and head movement by accelerometer in crossing obstacles, turning and stair walking
 

Secondary	
 
• Eye tracking characteristics
 
• Visual function
 
• Risk of fall
 
• Vision related quality of life
 
	
 
• Area of interest (heatmap) and gaze duration by eye tracking (Tobii pro2) during level ground obstacle crossing and stair walking
 
• Duration of Timed up and go test Visual acuity
 
• IOL rotation
 
• Fall efficacy scale and fear of falling
 
• CAT-PROM 5 questionnaire
 

Investigational Medicinal Product(s)	Monofocal Toric and non-Toric intraocular lens	
Formulation, Dose, Route of Administration	Artificial intraocular lens implantation during cataract correction surgery	

Vision and balance changes after bilateral implantation of Toric IOLs  
IRAS ID: 286913

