## **10. STATISTICS AND DATA ANALYSIS**

### **10.1 Sample size calculation**

Sample size test calculation was carried out with the G\*Power 3.1 program (Faul *et al.*, 2007) for comparison of the main outcome measure of dynamic balance (between IOL design) using mixed ANOVA (repeated measures, between factor being the type of IOL).

Based on of the dynamic balance measurement (JERK score) in a previous study (Mancini *et al.*, 2011) an estimated medium effect size (0.25) will be used. With a power of 85% and level of significance ( $p$ ) set at 0.05 and effect size of 0.25, 55 participants will be required in each group (Monofocal vs Toric IOL). Accounting for a 20% drop out rate, 70 participants will therefore be recruited in each group (A total of 140 participants).

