### 10.3.2 Primary outcome analysis- Dynamic stability in three functional activities

The following outcomes will be collected at three time points: before surgery, 3 to 6 months after first and second eye surgery.

Outcome measures	Data collected	Data type/ details	Quantitative Statistical Analysis
Dynamic stability during turning, obstacle crossing and stair walking	Accelerometers data (angular position and acceleration) of change in head tilting and centre of mass will be recorded  Performance of TU&G test	Interval  Centre of mass and head movement will be calculated using ProMove 3D (Inertia Technology, The Netherlands) and MATLAB.  The angular position, velocity and acceleration of the sensors will be tracked on each participant  Duration in seconds of TU&G test	The average reading of the 3 trials in each functional activity will be calculated.  Mixed ANOVA and post-hoc Bonferroni tests will be used to determine the differences between the Toric IOLs group and Monofocal IOLs group before surgery and 6 months after second eye surgery.

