### 10.3.3 Secondary outcome analysis

Outcomes	Data collected	Data type	Quantitative statistical Analysis
Eye glazing characteristics during obstacle crossing and stair walking	Gazing duration on obstacles and area of interest on environment during stair walking  Area of interest determined by heat map (area with highest frequency of gazing)	Interval  Gaze pattern of location of hotspots and duration of gaze will be collected using Tobii pro eye tracker.  % time spent on fixation of highlighted object or area of interest  Best performance among 3 trials will be used.	Mixed ANOVA and post-hoc Bonferroni tests will be used to determine the differences between the Toric IOLs group and Monofocal IOLs group before surgery and 6 months after second eye surgery.
Refraction and visual acuity	-Visual acuity (vision, sphere, Cylinder, Axis, DVA, Add NVA) -IOL tilt and decentration -IOL rotation (for Toric IOL group only)	Interval  Average tilt, decentration and rotation of lens will be analysed by calculating average value in Toric and monofocal groups. Bland Altman will be used to study the agreement of position-level of error for IOLs tilt, decentration and rotation.	Mixed ANOVA and post-hoc Bonferroni tests will be used to determine the differences between the Toric IOLs group and Monofocal IOLs group before surgery and 6 months after second eye surgery.  Unaided and aided distance visual acuity will be recorded in Log MAR and comparisons between the two lenses pre and post cataract surgery will be conducted using a two-way ANOVA. Post-operative refractive astigmatism will be analysed using the Alpins method*. Correlation between SIA and TIA will be assessed, and dependent t-tests will be used to analyse the remaining metrics in the two groups
Questionnaire	Short Fall Efficacy Scale International	Ordinal (non-parametric)	Mixed ANOVA and post-hoc Bonferroni tests will be used to determine the differences between the Toric IOLs group

Vision and balance changes after bilateral implantation of Toric IOLs  
IRAS ID: 286913

	Fear of Falling Questionnaire CAT-PROM 5 Quality of life Questionnaire		and Monofocal IOLs group before surgery and 6 months after second eye surgery.
--	---	--	--

\*Post-operative refractive astigmatism will be analysed using the Alpíns method. Cylindrical power and axis will be converted to vectors (J0 and J45; Equations 1 & 2).

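### Timed up-and-go is scored by two different rules (best of three in 7.6, average of three in 10.3.2) and the 'best' gaze trial in 10.3.3 is undefined; state one scoring rule per variable before unmasking

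*Combined protocol and SAP*

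**What the plan says.** Three places in the combined protocol and SAP say how three repeated trials become one score.

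- **Section 7.6 (Baseline data):** "Three trials will be taken to estimate the average and the best recorded time will be taken for the TUG test". Within this one sentence, averaging is the general aim and the best time is the rule for TUG.
- **Section 10.3.2 (Primary outcome analysis):** the single row lists accelerometer data and "Duration in seconds of TU&G test". Its analysis cell says: "The average reading of the 3 trials in each functional activity will be calculated". TUG is not excepted.
- **Section 10.3.3 (Secondary outcome analysis), gaze row:** "Best performance among 3 trials will be used". The row covers gaze duration, hotspot location from the heat map, and the percentage of "time spent on fixation of highlighted object or area of interest". It states no direction of benefit for any of them.

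The status of TUG also varies. The Trial Summary lists its duration among the secondary measures, while the tables in 10.3.1 and 10.3.2 place it under the primary outcome. The table in 10.3.1 puts eye-gaze characteristics under primary outcomes too, whereas 3.5 and 10.3.3 treat them as secondary.

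**The concern.** Two separate problems arise.

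For TUG, the plan gives two derivations of one variable. The shortest of three times is never longer than their mean, and is shorter whenever the three differ. The reported value therefore depends on which section the analyst follows, and that outcome sits in the primary analysis table.

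For gaze, the rule cannot be executed. A long fixation on an obstacle might mean careful attention or difficulty in seeing it, and the plan does not say which counts as good performance. Nor does it say whether one trial supplies every gaze metric or each metric has its own best trial. Someone must decide with the recordings in hand.

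Masking does not close that gap. Section 7.4 accepts that the visual assessment discloses the lens type, and deals with this by doing the stability tests first at post-surgery visits. That protects data collection within a visit, but nothing requires gaze trials to be selected before visual testing or by a masked person. If the same assessor sees a participant at visits 2 and 3, visual testing at visit 2 can also disclose the lens before visit 3. Under 14.2 one person is coordinator, data manager and outcome assessor. Under 14.1 the CI and co-investigators analyse the data, and under 7.3 the CI produces the allocation list.

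**Working it through.** **1. The scoring rules side by side**

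| Variable | 7.6 | 10.3.2 | 10.3.3 | Can it be run as written? |
|---|---|---|---|---|
| Sensor readings | average | average | – | yes |
| TUG time | best | average (no exception) | – | conflict |
| Gaze duration, % fixation time | – | – | best, no direction given | no |
| Hotspot location | – | – | best, but not a scalar | no |

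**2. The plan's own sample size**

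Inputs from 10.1: "an estimated medium effect size (0.25) will be used", 85% power, two-sided 0.05, 55 per group. The correlation between repeated measures is not stated; 0.5 is assumed here. The number of time points is m = 2, from the pre versus post factor in 10.3.

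For the between-group test in a repeated-measures ANOVA, the noncentrality is λ = f²·N·m / (1 + (m − 1)ρ).

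λ = 0.0625 × 110 × 2 / 1.5 = 9.17, with 1 and 108 degrees of freedom. Power is 0.851, so 55 per group is reproduced. Dropout: 55 / 0.8 = 68.75, rounded up to 69 per group (138 in total), against the plan's 70 and 140. The effect size is tied to a JERK score, not to TUG or gaze, so the scoring rule for those variables does not enter this figure.

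**3. Within-session error: best of three against the mean of three**

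Let σ² be the single-trial error variance, with independent trials. The mean has variance σ²/3 = 0.333σ² whatever the error distribution. The variance of the minimum depends on the shape (simulation, 2,000,000 sets of three):

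| Assumed error shape | Variance of best (× σ²) | Ratio to mean |
|---|---|---|
| Normal | 0.559 | 1.68 |
| Lognormal, log-SD 0.1 | 0.462 | 1.39 |
| Lognormal, log-SD 0.2 | 0.377 | 1.13 |
| Lognormal, log-SD 0.25 | 0.338 | 1.01 |
| Lognormal, log-SD 0.3 | 0.302 | 0.91 |
| Lognormal, log-SD 0.5 | 0.187 | 0.56 |
| Exponential | 0.111 | 0.33 |

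The penalty disappears at about log-SD 0.25 and reverses beyond it. The documents give no figure that places TUG times in this table. For gaze the comparison cannot be made at all until 'best' has a direction.

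**4. What the normal case would mean for total variance**

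This is an illustration for an outcome whose mean of three has f = 0.25. With total single-trial variance scaled to 1 and single-trial ICC as shown:

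- variance of the mean score = ICC + (1 − ICC)/3
- variance of the best score = ICC + (1 − ICC) × 0.5595
- f for the best score = 0.25 × √(variance of mean score / variance of best score)

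| Assumed ICC | Variance, mean | Variance, best | Ratio | Power at N = 110 |
|---|---|---|---|---|
| 0.5 | 0.667 | 0.780 | 1.17 | 0.792 |
| 0.7 | 0.800 | 0.868 | 1.08 | 0.821 |
| 0.8 | 0.867 | 0.912 | 1.05 | 0.833 |
| 0.9 | 0.933 | 0.956 | 1.02 | 0.843 |

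So even under normal errors the 68% applies to within-session error only. Total variance rises by 2% to 17%, and power falls from 0.851 by about 1 to 6 points.

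**The case against.** The strongest reply is that 7.6 is coherent by itself: sensor readings are averaged and TUG, as the specific case, takes the best time. Section 10.3.2 speaks of an average reading per functional activity, which fits accelerometer output, so 7.6 could be an exception that 10.3.2 forgot to repeat. That reading is fair, and it may be what was meant. But 10.3.2 lists TUG duration in the same row and carries no exception, so the sections still have to be reconciled.

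A reader might infer more than the documents support:

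- **That best-of-three makes the data noisier.** This depends on the error shape. Right skew is plausible for timed tests, and it shrinks and then reverses the penalty.
- **That steadier performance in one arm would bias the TUG comparison.** Under normal errors the best time lies 0.846σ below the average, so a 20% fall in σ in one arm would move it by 0.2 × 0.846σ = 0.17σ. Nothing in the documents suggests such a fall. A shift common to both arms cancels, and a faster best time through steadier performance could be a real benefit.
- **That TUG trials could be picked selectively.** The shortest of three times is mechanical. The room for choice exists for gaze only.
- **That the mean is the only valid TUG score.** A pre-specified best time would remove the contradiction equally well.

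**Conclusion.** The point stands as one of pre-specification. TUG duration has two scoring rules that can give different values, and its primary or secondary status is inconsistent. The gaze rule is undefined and leaves the scored trial open to choice after the data are seen, possibly with the lens type known. These conclusions rest on the text alone.

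No size can be put on a loss of precision. The 1.68 ratio holds only for independent normal trial errors, and the power figures also assume an ICC and that f = 0.25 applies to the mean score. The sample size of 110 evaluable and 140 recruited does not change. This is a minor point, worth correcting because the correction is so cheap.

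**What to change.** 1. **TUG:** state one rule, in the same words, in 7.6 and 10.3.2. The mean of all valid trials is a sensible default because 10.3.2 already uses it; keep the best time as a sensitivity analysis. Give TUG one status, primary or secondary, throughout.
2. **Scalar gaze metrics:** in 10.3.3, replace the best-performance rule with the mean of all valid trials for gaze duration and percent fixation time. This needs no direction of benefit and removes the choice of trial.
3. **Hotspot location:** give it its own rule, such as pooling all valid trials into one heat map, since a location cannot be averaged like a duration.
4. **Valid trials:** define a valid trial and say what is done with fewer than three. Without this, the mean would bring in new discretion.
5. **Timing:** fix these rules before unmasking.

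The cost is a few wording changes and a short definition. Three trials are already planned, and 10.3.1 provides for files saved by trial number, so no extra testing is needed. The case report form is not among the documents; if it holds only the best TUG time, it needs space for all three. If the mean is adopted, the main TUG result is slightly less comparable with work that reports best times, and the sensitivity analysis covers that.

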## 7.7 Trial assessments

Three study visits will be arranged for each participant who have given written informed consent to take part in the study.

**Study visit 1:** Pre-surgery baseline assessment will take place at the PAHC building of UoP, at least one week before the cataract surgery. After the participants have the cataract screening appointment at REI, they usually wait 3 to 6 weeks before the cataract surgery. The first study visit for the pre-operation baseline assessment will be arranged during this period. This also gives participants extra time to reconsider taking part in the study from when they signed the informed consent form at the REI. The study coordinator will reconfirm informed consent over the phone or by email (whichever is the preferred contact method) with the participant before arranging the first study visit and at the start of each study visit. If a participant needs to delay or cancel the cataract surgery due to a medical reason, the study coordinator will liaise with the PI who is the Ophthalmologist to confirm the participant is still suitable to take part in the study.

Intervention: participants will be randomized into two groups. One group will receive Toric Monofocal IOLs and the other group will receive standard non-Toric Monofocal IOLs.

**Study visit 2:** Reassessment of outcome measures will take place three to six months after first eye surgery at the PAHC building of UoP.

**Study visit 3:** Reassessment of outcome measures will take place three to six months after second eye surgery at the PAHC building of UoP.

## 7.8 Long term follow-up assessments/ lost to follow-up

There is no long term follow up assessments. If the participants miss their scheduled study visit, they will be contacted by telephone or email (depending on their indicated preference). If no response, two more attempts within 2 months will be made. Participants who are not contactable will be marked as lost to follow-up and notification sent to their GP and the PI for their medical records. A notification letter will be sent to the participants' address or email account.

Vision and balance changes after bilateral implantation of Toric IOLs  
 IRAS ID: 286913

### 7.9 Withdrawal criteria

The participants can withdraw from the study at any time without giving any reason. Should there be a requirement to reassess eligibility, the PI or study coordinator may withdraw the participant if they do not meet the inclusion/exclusion criteria.

### 7.10 End of trial

The third study visit (3 to 6 months after the second eye cataract surgery) is the last contact with the participant. Upon completion of the last study visit for all 140 recruited participants (unless they have withdrawn) will be the end of the trial.

## 8. TRIAL TREATMENTS

### 8.1 Name and description of investigational medicinal product(s)

Arms	Product name	Further information
Intervention arm	Monofocal Toric IOLs: Zeiss AT TORBI	This is a CE marked medical device which has market approval and is being used according to its intended use
Control arm	Standard Monofocal non-Toric IOLs: Zeiss CT ASPHINA	This is a CE marked medical device which has market approval and is being used according to its intended use

### 8.2 Regulatory status of the device

Control arm: Zeiss monofocal intraocular lens. This has a marketing authorisation (MA) in the UK and is being used in its marketed presentation and packaging bearing the MA number.

Intervention arm: Zeiss Toric intraocular lens. This has a marketing authorisation (MA) in the UK and is being used in its marketed presentation and packaging bearing the MA number.

Both IOLs are regulated by the Medicines and Healthcare products Regulatory Agency UK (MHRA) and compliant with both the Medical Devices Regulations 2002 (SI 2002 No 618, as amended) and the General Product Safety Regulations 2005 (SI 2005 No 1803). Although Toric IOLs are not used in UHP but the PI has used both IOLs for cataract surgeries in other hospital in UK.

Vision and balance changes after bilateral implantation of Toric IOLs  
IRAS ID: 286913

### 8.3 Product Characteristics

Products	Characteristics
Monofocal Toric IOLs: Zeiss AT TORBI	Monofocal Toric IOLs with bitoric and aberration-neutral design offering precise correction of astigmatism and achieving spectacle-free distance vision. It is made of hydrophilic acrylic material with hydrophobic surface properties. It is a one-piece plate-haptic construction with four-point fixation for exceptional rotational stability. It is implanted into the capsular bag of the eye through a small incision.
Standard Monofocal non-Toric IOLs: Zeiss CT ASPHINA	Standard monofocal IOLs used in most of the cataract correction surgery. Similar to the Toric, it is made of hydrophilic acrylic material with hydrophobic surface properties. It is also a one-piece plate-haptic construction with four-point fixation and is implanted into the capsular bag of the eye through a small incision.

\*Link to technical specifications of all model of Zeiss IOLs  
[https://www.zeiss.com/content/dam/med/ref\\_international/products/iols-injectors-bss-ovd/ovd/pdf/iol-ovd-portfolio.pdf](https://www.zeiss.com/content/dam/med/ref_international/products/iols-injectors-bss-ovd/ovd/pdf/iol-ovd-portfolio.pdf)

